**CONFIDENTIAL**

202090 (EBOLA Z CHAD3-004)  
Protocol Amendment 2 Final

EUA:	Emergency Use Authorization
EVD:	Ebola Virus Disease
FDA:	Food and Drug Administration
GCP:	Good Clinical Practice
GMT:	Geometric Mean Titre
GP:	Glycoprotein
GSK:	GlaxoSmithKline
HAART:	Highly Active Anti-retroviral Therapy
HIV:	Human Immunodeficiency Virus
HPLC:	High Performance Liquid Chromatography
IAF:	Informed Assent Form
IB:	Investigator Brochure
ICF:	Informed Consent Form
ICH:	International Conference on Harmonisation
ICS:	Intracellular Cytokine Staining
IDMC:	Independent Data Monitoring Committee
EC:	Independent Ethics Committee
IM:	Intramuscular
IND:	Investigational New Drug
IRB:	Institutional Review Board
IVRS:	Interactive Voice Response System
IWRS:	Interactive Web Response System
LAR:	Legally Acceptable Representative
LMP:	Last Menstrual Period
MACDP:	Metropolitan Atlanta Congenital Defects Program
MedDRA:	Medical Dictionary for Regulatory Activities

**CONFIDENTIAL**

202090 (EBOLA Z CHAD3-004)  
Protocol Amendment 2 Final

MenACWY-TT:	Meningococcal Serogroups A, C, W-135, Y Tetanus Toxoid Conjugate vaccine
NA:	Not Applicable
NaCl:	Sodium Chloride
NVITAL:	NIAID Vaccine Immune T-cell and Antibody Laboratory (NIH)
PBMCs:	Peripheral Blood Mononuclear Cells
PSA:	Neisseria meningitidis Serogroup A Polysaccharide
PSC:	Neisseria meningitidis Serogroup C Polysaccharide
PSRI:	Periodic Safety Report Information
PSW:	Neisseria meningitidis Serogroup W-135 Polysaccharide
PsY:	Neisseria meningitidis Serogroup Y Polysaccharide
qPCR:	Quantitative Polymerase Chain Reaction
RDT:	Rapid Diagnostic Test
RESTV:	Ebola Virus Reston
RNA:	Ribonucleic Acid
SAE:	Serious Adverse Event
SmPC:	Summary of Product Characteristics
SOP:	Standard Operating Procedure
SUDV:	Ebola Virus Sudan
TAFV:	Ebola Virus Taï Forest
TVC:	Total Vaccinated Cohort
US:	United States
UK:	United Kingdom
vp:	Viral Particles
VRC/NIAID:	Vaccine Research Center of the National Institute of Allergy and Infectious Diseases

**WHO:**

World Health Organisation

## GLOSSARY OF TERMS

- Adequate contraception:** Adequate contraception is defined as a contraceptive method with failure rate of less than 1% per year when used consistently and correctly and when applicable, in accordance with the product label for example:
- abstinence from penile-vaginal intercourse, when this is their preferred and usual lifestyle,
  - oral contraceptives, either combined or progestogen alone,
  - injectable progestogen,
  - implants of etenogestrel or levonorgestrel,
  - estrogenic vaginal ring,
  - percutaneous contraceptive patches,
  - intrauterine device or intrauterine system,
  - male partner sterilisation prior to the female subject's entry into the study, and this male is the sole partner for that subject,
- The information on the male sterility can come from the site personnel's review of the subject's medical records; or interview with the subject on her medical history.
- male condom combined with a vaginal spermicide (foam, gel, film, cream or suppository),
  - male condom combined with a female diaphragm, either with or without a vaginal spermicide (foam, gel, film, cream, or suppository).
- Adequate contraception does not apply to subjects of childbearing potential with same sex partners, when this is their preferred and usual lifestyle.

- Adverse event:** Any untoward medical occurrence in a patient or clinical investigation subject, temporally associated with the use of a medicinal product, whether or not considered related to the medicinal product.
- An adverse event (AE) can therefore be any unfavourable and unintended sign (including an abnormal laboratory finding), symptom, or disease (new or exacerbated) temporally associated with the use of a medicinal product. For marketed medicinal products, this also includes failure to produce expected benefits (i.e., lack of

efficacy), abuse or misuse.

**Blinding:**

A procedure in which one or more parties to the trial are kept unaware of the treatment assignment in order to reduce the risk of biased study outcomes.

Observer-blind means that the subject and the vaccination centre and sponsor personnel involved in the clinical evaluation of the subjects are blinded while other study personnel may be aware of the treatment assignment.

Single-blind means that vaccination centre and sponsor personnel are aware of the treatment assignment but the subject is not.

**Child in care:**

A child who has been placed under the control or protection of an agency, organisation, institution or entity by the courts, the government or a government body, acting in accordance with powers conferred on them by law or regulation. The definition of a child in care can include a child cared for by foster parents or living in a care home or institution, provided that the arrangement falls within the definition above. The definition of a child in care does not include a child who is adopted or has an appointed legal guardian.

**Eligible:**

Qualified for enrolment into the study based upon strict adherence to inclusion/exclusion criteria.

**Epoch:**

An epoch is a self-contained set of consecutive timepoints or a single timepoint from a single protocol. Self-contained means that data collected for all subjects at all timepoints within that epoch allows to draw a complete conclusion to define or precise the targeted label of the product. Typical examples of epochs are primary vaccinations, boosters, yearly immunogenicity follow-ups, and surveillance periods for efficacy or safety.

**eTrack:**

GlaxoSmithKline's (GSK's) tracking tool for clinical trials.

**Evaluable:**

Meeting all eligibility criteria, complying with the procedures defined in the protocol, and, therefore, included in the according-to-protocol (ATP) analysis (see [Sections 6.7.2](#) and [11.5](#) for details on criteria for evaluability).

Investigational vaccine:  (Synonym of Investigational Medicinal Product)	A pharmaceutical form of an active ingredient or placebo being tested or used as a reference in a clinical trial, including a product with a marketing authorisation when used in a way different from the approved form, or when used for an unapproved indication, or when used to gain further information about an approved use.
Menarche:	Menarche is the onset of menses for the first time in a young female and is preceded by several changes associated with puberty including breast development and pubic hair growth. Menarche usually occurs within 1 to 2 years of breast development, thelarche. However, a young female can become pregnant before her first menses. Thus, a conservative definition of non-childbearing potential in a pre-menarcheal female is a young female who has not yet entered puberty as evidenced by lack of breast development (palpable glandular breast tissue).
Protocol amendment:	The International Conference on Harmonisation (ICH) defines a protocol amendment as: 'A written description of a change(s) to or formal clarification of a protocol.' GSK Biologicals further details this to include a change to an approved protocol that affects the safety of subjects, scope of the investigation, study design, or scientific integrity of the study.
Protocol administrative change:	A protocol administrative change addresses changes to only logistical or administrative aspects of the study.
Randomisation:	Process of random attribution of treatment to subjects in order to reduce bias of selection.
Self-contained study:	Study with objectives not linked to the data of another study.
Solicited adverse event:	Adverse events to be recorded as endpoints in the clinical study. The presence/occurrence/intensity of these events is actively solicited from the subject or an observer during a specified post-vaccination follow-up period.
Sub-cohort:	A group of subjects for whom specific study procedures are planned as compared to other subjects.
Subject:	Term used throughout the protocol to denote an individual who has been contacted in order to participate or participates in the clinical study, either as a recipient of the vaccine or as a control.

Subject number:	A unique number identifying a subject, assigned to each subject consenting to participate in the study.
Subset:	A subset is defined as a group of subjects for which additional assays are planned as compared to other subjects.
Treatment:	Term used throughout the clinical study to denote a set of investigational product(s) or marketed product(s) or placebo intended to be administered to a subject, identified by a unique number, according to the study randomisation or treatment allocation.
Treatment number:	A number identifying a treatment to a subject, according to the study randomisation or treatment allocation.
Unsolicited adverse event:	Any AE reported in addition to those solicited during the clinical study. Also any 'solicited' symptom with onset outside the specified period of follow-up for solicited symptoms will be reported as an unsolicited adverse event.

**TRADEMARKS**

The following trademarks are used in the present protocol.

Note: In the body of the protocol (including the synopsis), the names of the vaccines will be written without the superscript symbol ® and in *italics*.

Trademarks of the GlaxoSmithKline group of companies	Generic description
Nimenrix®	Meningococcal A, C, W-135 & Y vaccine

## 1. INTRODUCTION

### 1.1. Background

#### 1.1.1. Ebola virus Zaire outbreak 2014

The EVD outbreak in West Africa was first recognised on 22 March 2014 in Guinea. By 02 December 2014, the epidemic had spread to Sierra Leone and Liberia, with a total of 17 256 cases in those 3 countries (including 6 113 deaths). Travel-associated cases were observed in Mali, Senegal, Nigeria, Spain and United States (US), with localised transmission in Nigeria, Spain and US. The outbreaks of EVD in Senegal and Nigeria were declared over on 17 October and 19 October 2014, respectively. While children have been described as being less at risk of contracting of EVD [McElroy, 2014], it has been estimated that about 18% of cases in the current outbreak were people under 15 years of age [World Health Organisation (WHO) Ebola Response Team, 2014].

#### 1.1.2. Ebola virus and Zaire Ebola virus disease

The genus Ebola virus is one of 3 genera in the family Filoviridae, which along with the genera, Marburgvirus and Cuevavirus, are known to induce viral haemorrhagic fever. The 5 distinct species included in the genus Ebola virus are Bundibugyo (BDBV), Reston (RESTV), Sudan (SUDV), Taï Forest (TAFV), and Zaire (EBOV).

Ebola virus is a large, negative-strand ribonucleic acid (RNA) virus composed of 7 genes encoding viral proteins, including a single glycoprotein (GP). The virus is responsible for causing EVD in humans. In particular, BDBV, EBOV, and SUDV have been associated with large outbreaks of EVD in Africa and reported case fatality ratios of up to 90% (WHO, 2014a). Transmission of Ebola virus to humans is not yet fully understood, but is likely due to incidental exposure to infected animals. EVD then spreads through human-to-human transmission, with infection resulting from direct contact with blood, secretions, organs or other bodily fluids of infected people, and indirect contact with environments contaminated by such fluids.

EVD has an incubation period of 2 to 21 days (mean 4 to 10) which is followed by an abrupt onset of non-specific symptoms such as fever, chills, malaise, and myalgia. The subsequent signs and symptoms indicate multisystem involvement and include systemic (prostration), gastrointestinal (anorexia, nausea, vomiting, abdominal pain, diarrhoea), respiratory (chest pain, shortness of breath, cough, nasal discharge), vascular (conjunctival infection, postural hypotension, oedema), and neurological (headache, confusion, coma) manifestations. Haemorrhagic manifestations consistent with disseminated intravascular coagulation arise during the peak of the illness and include petechiae, ecchymoses, uncontrolled oozing from venepuncture sites, mucosal haemorrhages, and post-mortem evidence of visceral haemorrhagic effusions. A macropapular rash associated with varying severity of erythema and desquamate can often be noted by day 5 to 7 of the illness; this symptom is a valuable differential diagnostic feature and is usually followed by desquamation in survivors. Abdominal pain is sometimes associated with hyperamylasaemia and true pancreatitis. In later stages, shock, convulsions, severe metabolic disturbances, and, in more than half the cases,

diffuse coagulopathy supervene. Laboratory findings include low white blood cell and platelet counts and elevated liver enzymes. In general, the symptoms last for about 7 to 14 days, after which recovery may occur. Death can occur 6 to 16 days after the onset of symptoms [Feldmann, 2011]. People are infectious as long as their blood and secretions contain the virus; the virus was isolated from semen 61 days after onset of illness in a man who was infected in a laboratory [WHO, 2014b].

### **1.1.3. GlaxoSmithKline Biologicals' investigational ChAd3-EBO-Z vaccine**

The replication-defective investigational EBOV vaccine encoded by chimpanzee-derived adenovirus (ChAd3-EBO-Z) was developed by the Vaccine Research Center of the National Institute of Allergy and Infectious Diseases (VRC/NIAID) in the US using the ReiThera (formerly known as Okairos) adenovirus vaccine platform technology, which was acquired by GSK Biologicals in May 2013. The DNA fragment inserted in the chimpanzee adenovirus type 3 (ChAd3) vector encodes the EBOV GP, which is expressed on the virion surface and is critical for attachment to host cells and catalysis of membrane fusion. A single dose of  $10^{10}$  viral particles (vp) of ChAd3-EBO-Z provided 100% protection 4 to 5 weeks after vaccination in cynomolgous macaques [Stanley, 2014].

Serological studies showed a low seroprevalence in human sera for antibodies to ChAd3, and when present, antibody titres were low [Colloca, 2012]. Adenovirus type 5 (Ad5; a common adenovirus infection of humans) pre-existing immunity did not appear to cross-react with ChAd3 in mice [Peruzzi, 2009]. ChAd3-based vaccines were capable of inducing an immune response and protection comparable to human Ad5 vectored vaccine even in those with pre-existing immunity against Ad5.

Please refer to the current Investigator Brochure (IB) for information regarding the pre-clinical and clinical studies of ChAd3-EBO-Z.

## **1.2. Rationale for the study and study design**

### **1.2.1. Rationale for the study**

On 7 August 2014, the WHO requested that GSK “fully engages in WHO-coordinated efforts to test, license and make available safe and effective Ebola interventions” to assist in the control of the outbreak in Western Africa. Given the severity of the situation, time to vaccine deployment was an important aspect of the WHO request. In response to this call, an accelerated Phase 1, dose-finding vaccine development effort was initiated mid-August that involved WHO, GSK, VRC/NIAID, the University of Oxford, the University of Maryland and the University of Lausanne and the Centre for Vaccine Development in Mali.

Although health care workers will be priority vaccination targets, mass vaccination strategies may be developed as one of the ways to protect populations and contain the epidemics. In this context, children will need to be vaccinated too. The present Phase 2, randomised, controlled trial will aim at collecting safety and immunogenicity data following a single intramuscular (IM) dose of the investigational ChAd3-EBO-Z vaccine.

The study will be conducted in healthy children living in countries adjacent to the current Ebola outbreak zones. In parallel with the current study, the safety and immunogenicity of the investigational ChAd3-EBO-Z vaccine will be assessed in healthy adults living in countries adjacent to the current Ebola outbreak (study EBOLA Z CHAD3-005). Study EBOLA Z CHAD3-005 will start before the current study as to collect safety and reactogenicity data in 100 adults, after 1 week of follow-up, living in countries adjacent to the current Ebola outbreak before proceeding to vaccination of children.

## 1.2.2. Rationale for the study design

### 1.2.2.1. Investigational ChAd3-EBO-Z vaccine dose

Dose selection for paediatric use *was* based on information derived from dose-range studies conducted with the ChAd3-EBO-Z vaccine candidate in adults and on past experience with other recombinant adenovirus-based candidate vaccines. ***(Amended 06 May 2015.)***

While investigational ChAd3-based candidate vaccines have not been administered to children before, other recombinant adenovirus-based candidate vaccines have been administered to children without safety concerns. A ChAd63 ME-TRAP malaria candidate vaccine has been safely administered to healthy adults in United Kingdom (UK) and Kenya, and to healthy infants and children in The Gambia and Burkina Faso. The IM dose of  $5 \times 10^{10}$  vp was determined to be optimal in both adults and children [Afolabi, 2012; Ogwang, 2013; O'Hara, 2012; ClinicalTrials.gov NCT01635647; ClinicalTrials.gov NCT02083887; [name], *personal communication*]. In the tuberculosis vaccine research field, up to two dose of  $1 \times 10^{11}$  vp of AERAS-402, a recombinant, replication-defective adenovirus type 35 expressing tuberculosis antigens, the highest dose evaluated, showed favourable safety in infants 6 to 9 months old [Kagina, 2014]. This dose is also used in adults [ClinicalTrials.gov NCT01683773].

Importantly, dose ranging in terms of vp is classically done on a logarithmic scale while arithmetic scales are usually used to describe weight differences between adults and children. In other words, the variability in weight between adults and children is small as compared to classical dose ranging in terms of number of vp, and inherent imprecision/ variability in number of vp.

Four different investigational vaccine doses are currently being evaluated for safety, reactogenicity and immunogenicity in adults in Phase 1 studies. ***Based on data from these studies, the  $1 \times 10^{11}$  vp dose was selected for further assessment in Phase 2 and Phase 3 clinical studies in adults. This dose was determined using a high performance liquid chromatography (HPLC) analytical method for the vaccine lots used in the Phase 1 studies. The same dose will be used in this paediatric study. However, depending on the recommendation of the independent data monitoring committee (IDMC), a lower dose may be selected based on safety and reactogenicity data accrued during the age de-escalation process for children in younger age strata. It should be noted that the analytical method (quantitative polymerase chain reaction [qPCR]) that measures the concentration of virus particles per mL (vp/mL) present in the ChAd3-EBO-Z vials used in the current paediatric study is different***

*from the analytical method (HPLC) used for the Phase 1 studies. As a result, a dose of  $2 \times 10^{11}$  vp will be used in this study, to administer the equivalent of the  $1 \times 10^{11}$  vp dose that was shown to be optimal in Phase 1 studies.* As for other recombinant adenovirus-based vaccine candidates which showed adequate safety upon the use of adult doses in children as explained above, it is currently proposed that the same vaccine dose will be assessed *in children 1 to 17 years of age* in this study. However, a lower vaccine dose may be selected for children of younger age groups based on the safety and reactogenicity data accrued during the age de-escalation process. *(Amended 06 May 2015.)*

*As this study is conducted in Malaria endemic regions and the presence of Malaria infection may adversely affect the safety and immunogenicity evaluations of the investigational ChAd3-EBO-Z vaccine, all subjects will be tested for Malaria infection using a rapid diagnostic test (RDT) procedure during Screening. Subsequently, all subjects diagnosed with Malaria will receive antimalarial treatment according to local/ national standards (e.g., a 3-day treatment course of artemisinin-based combination therapy), during the Screening period. Hence, only subjects for whom the RDT was negative, or for whom the RDT was positive and who received a complete course of antimalarial treatment during the Screening period can be considered for study participation. (Amended 06 May 2015.)*

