#### **Other benefits**

***All subjects who provide informed consent for study participation will be tested for Malaria infection using an RDT procedure at the time of Screening. Subjects who are diagnosed with Malaria will receive antimalarial treatment according to local/ national standards (e.g., a 3-day treatment course of artemisinin-based combination therapy), during the Screening period, to clear the infection prior to vaccination. (Amended 06 May 2015.)***

Another benefit for the subjects may include the gaining of information about their general health status through the medical evaluations/ assessments associated with this study (physical examination, blood testing [haematology and biochemistry data]). All subjects participating to the Screening Visit of this study will be medically examined including testing for haematological (complete blood count [CBC], including differential count and platelet count) and biochemical (alanine aminotransferase [ALT] and creatinine) parameters. Those subjects with clinically significant disease who are not eligible for study participation will be referred for medical care to local facilities. Those subjects who are eligible and participate in the study will receive medical follow-up during the study.

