  - *A blood sample (fingerprick) will be taken at Screening for Malaria RDT. (Amended 06 May 2015.)*
  - Blood samples for **haematology/ biochemistry** assessment will be taken from all subjects at Screening, at the Day 3, Day 6, the Day 30, the Month 6, the Month 6 + 6 days, the Month 6 + 30 days, and the Month 12 visits.
  - Blood samples for **humoral immunity** will be taken from all subjects at the Day 0, the Day 30, the Month 6, the Month 6 + 30 days, and the Month 12 visits.
  - Blood samples for **CMI** will be taken from a sub-cohort of 90 subjects per group (30 children per age stratum per group) at the Day 0, the Day 30, the Month 6, the Month 6 + 30 days, and the Month 12 visits.
- **Type of study:** self-contained.
- **Data collection:** eSource.
- **Safety monitoring:** An IDMC will be appointed to monitor the safety and tolerability of the investigational ChAd3-EBO-Z vaccine. The IDMC will consist of clinical experts and a statistician who are not involved in the conduct of the study. Refer to [Section 9.10](#) for detailed description of the safety monitoring.

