#### **5.4. General study aspects**

Supplementary study conduct information not mandated to be present in this protocol is provided in the accompanying manuals. The manuals provide the Investigator and the site personnel with administrative and detailed technical information that does not impact the safety of the subjects.

**5.5. Outline of study procedures****5.5.1. List of study procedures****Table 5 List of study procedures during visits to the vaccination centre (Amended 06 May 2015)**

Type of contact	Visit	Visit	Visit	Visit	Visit	Contact *	Visit	Visit	Visit	Contact *	Visit
Timepoint	Screening 	Day 0 	Day 3	Day 6	Day 30	Month 3	Month 6	Month 6 + 6 days	Month 6 + 30 days	Month 9	Month 12
Informed consent	•										
Informed assent 	•										
RDT for Malaria	•										
Malaria treatment 	•										
Inclusion/exclusion criteria 	•	•									
Demographic data	•										
Medical history 	•	•									
Physical examination (including vital signs  )	• 	• 	0	0	0		•	0	0		0
Pregnancy test 	•	• 					•				
Pre-vaccination body temperature		•					•				
Check contraindications to vaccination		0					0				
Study group and treatment name allocation 		0					0				
Vaccination		•					•				
Recording of administered treatment number		0					0				
30 minutes post-vaccination observation		0					0				
Blood sampling:											
Blood for haematology/ biochemistry	• 		•	•	•		•	•	•		•
Blood for humoral immunity		•			•		•		•		•
Blood for CMI 		•			•		•		•		•
Safety assessment:											
Record solicited AEs (day 0 to day 6)		•	•	•			•	•			
Record unsolicited AEs (day 0 to day 29)		•	•	•	•		•	•	•		
Record AEs of specific interest (clinical symptoms of thrombocytopenia)			•	•							
Record SAEs	• 	•	•	•	•	•	•	•	•	•	•
Record pregnancies		•	•	•	•	•	•	•	•		

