**6. STUDY VACCINES/ PRODUCTS AND ADMINISTRATION (AMENDED 06 MAY 2015.)****6.1. Malaria treatment (Amended 06 May 2015.)**

*All subjects diagnosed with Malaria during Screening will receive antimalarial treatment according to local/ national standards (e.g., a 3-day treatment course of artemisinin-based combination therapy), during the Screening period.*

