## 6.6. Contraindications to vaccination

The following event constitutes a contraindication to study vaccination at that point in time; if this event occurs at the time scheduled for vaccination, the subject may be vaccinated at a later date, within the allowed time window:

- Acute disease and/ or fever at the time of vaccination.
  - Fever is defined as temperature  $\geq 37.5^{\circ}\text{C}/99.5^{\circ}\text{F}$ . Body temperature will be measured axillary.

The following events constitute absolute contraindications to subsequent vaccination. If any of these events are applicable at Month 6 the subject must not be vaccinated, but may continue other study procedures at the discretion of the Investigator:

- Anaphylaxis following vaccine administration.
- Clinically significant immunosuppressive or immunodeficient condition (*e.g.*, AIDS).
- Pregnancy (see [Section 9.2](#)).

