### 11.2. Secondary endpoint

- Anti-GP EBOV antibody titres, as measured by enzyme-linked immunosorbent assay (ELISA):
  - At Day 0 and Day 30, in all subjects, in both groups.
  - At Month 6 and Month 6 + 30 days, in all subjects, in the Group MENACWY-TT/ EBO-Z.

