### **11.8. Analysis of safety**

The analysis will be performed on the TVC.

All analyses will be descriptive. Analyses will be performed by age stratum (1 to 5 years, 6 to 12 years, 13 to 17 years) and overall.

In a first step, the safety results will be presented by treatment administered at Day 0 (ChAd3-EBO-Z vaccine [300 subjects] versus *Nimenrix* [300 subjects]). In a second step, all **available** data post-vaccination with the investigational ChAd3-EBO-Z vaccine (ChAd3-EBO-Z vaccine at Day 0 [300 subjects] and ChAd3-EBO-Z vaccine at Month 6 [300 subjects]) will be pooled (600 subjects). The latter aggregated data cannot be presented versus control because of the administration of the investigational ChAd3-EBO-Z vaccine to the children in the Group MENACWY-TT/ EBO-Z, who initially received *Nimenrix* (population overlap).

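### Half of the pooled ChAd3-EBO-Z recipients are dosed 5 to 8 months after the only malaria test, and SAP v2.0 shows their solicited and unsolicited adverse events only inside the pool

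*Protocol*

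**What the plan says.** The rationale in Protocol Section 1.2.2.1 is that "the presence of Malaria infection may adversely affect the safety and immunogenicity evaluations of the investigational ChAd3-EBO-Z vaccine". Section 1.3.2 (Other benefits) says treatment is given "during the Screening period, to clear the infection prior to vaccination", and does not limit this to the first vaccination.

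The procedures are tied to study entry. Section 3 states: "A blood sample (fingerprick) will be taken at Screening for Malaria RDT". In Table 5 (Section 5.5.1) the row "RDT for Malaria" is marked at Screening only. Section 6.1 reads: "All subjects diagnosed with Malaria during Screening will receive antimalarial treatment according to local/ national standards". The inclusion criterion in Section 4.3 counts back from randomisation. At Month 6 the visit includes temperature, physical examination, a haematology sample and a contraindication check. The temporary contraindication in Section 6.6 is "Acute disease and/ or fever at the time of vaccination".

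Group MENACWY-TT/EBO-Z receives Nimenrix at Day 0 and ChAd3-EBO-Z at Month 6; the other group has the reverse order. The primary AE endpoints (Section 11.1) cover each vaccination in both groups. The secondary endpoint (Section 11.2) includes anti-GP "At Month 6 and Month 6 + 30 days, in all subjects, in the Group MENACWY-TT/ EBO-Z". Section 11.8 presents results by Day 0 treatment first. The data after either ChAd3-EBO-Z dose then "will be pooled (600 subjects" in total, 300 per occasion); Section 11.9 does the same for immunogenicity.

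SAP v2.0 restricts the solicited and unsolicited AE incidence tables to events after the Day 0 vaccination unless otherwise specified, and repeats them for the pooled ChAd3-EBO-Z data (Sections 15.1.2 and 15.2.2). Malaria test results appear in a listing (Section 15.4). No subgroup analysis is planned (Section 7.5).

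**The concern.** In Group MENACWY-TT/EBO-Z the malaria screen comes before Nimenrix, although the protocol's stated worry is about evaluating ChAd3-EBO-Z. By the time this group receives ChAd3-EBO-Z, its malaria status is months out of date. A child with an afebrile, undiagnosed infection would pass the Section 6.6 check.

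Symptomatic background illness at Month 6 overlaps with the reactogenicity endpoints, fever above all. The natural safeguard is to look at the Month 6 doses separately and against the children given Nimenrix at the same visit. The AE tables described in SAP v2.0 allow neither. What is at stake is how the pooled safety result is read, and whether the primary AE endpoints are reported after each vaccination in both groups as defined.

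**Working it through.** **Age of the malaria test at the Month 6 dose.** Table 6 allows 0 to 30 days from Screening to Day 0, and 6 months ± 30 days from Day 0 to Month 6, which is about 5 to 7 months. Added together, the test is about 5 to 8 months old. At Day 0 a negative test is at most 30 days old.

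**Share of the pool.** 300 / (300 + 300) = 50% on planned numbers, and 100 / 200 = 50% in each age stratum.

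**The plan's own precision figures.** Exact (Clopper-Pearson) 95% intervals with n = 300 reproduce all seven rows of Protocol Table 22. For example, 15 events give 0.0283 to 0.0811 and 50 events give 0.1263 to 0.2138. Each vaccine-by-occasion column would have about 300 children, so it would carry the precision the plan already quotes for a group.

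**Where solicited and unsolicited AEs appear under SAP v2.0, Sections 15.1.2 and 15.2.2:**

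| Vaccine and occasion | Unpooled incidence tables | Pooled incidence tables |
|---|---|---|
| ChAd3-EBO-Z, Day 0 | shown | included |
| Nimenrix, Day 0 | shown | not included |
| ChAd3-EBO-Z, Month 6 | excluded | included, merged with Day 0 |
| Nimenrix, Month 6 | excluded | not included |

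There are three qualifications. SAE tables are split by vaccine (Section 15.1.5), so serious events after Month 6 Nimenrix are counted, but not by occasion. The table of AEs in at least 5% of subjects (Section 15.3) does not say which vaccination it covers. AEs of specific interest are collected after Day 0 only.

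**What pooling does.** With equal numbers, pooled rate = (Day 0 rate + Month 6 rate) / 2, so a difference δ between occasions moves the pooled rate by δ / 2. As an illustration from two rows of Table 22, take 15/300 (5.0%) at Day 0 and 50/300 (16.7%) at Month 6. The pool is 65/600 = 10.8%. This is above the upper limit for Day 0 (8.1%) and below the lower limit for Month 6 (12.6%), so it describes neither occasion.

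**Scale if malaria did act (all inputs assumed).** The documents give no prevalence. If 5% to 40% of the 300 were infected at Month 6, 300 × 0.05 = 15 to 300 × 0.40 = 120 children would be dosed while infected, or 2.5% to 20% of the 600. If infection added 10 to 20 percentage points to an AE rate, the Month 6 rate would rise by 0.05 × 10 = 0.5 to 0.40 × 20 = 8 points, and the pooled rate by 0.25 to 4 points. That the effect is an increase is itself an assumption.

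**The case against.** The case on the other side has real weight.

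- **The trial has a comparator.** Children given Nimenrix at Month 6 attend the same visit, are equally untested, and have the same AE and haematology follow-up. Clinical malaria in the 30 days after a dose would be recorded as an AE and its treatment as concomitant medication. A reader might infer that no recorded data can separate malaria from vaccine effects at Month 6; the documents do not support that. Only symptom-free infection at dosing goes unrecorded.
- **Much is already split.** Anti-GP results are given by group and timepoint (Protocol Section 11.9; SAP v2.0 Section 14.1.1), so the Month 6 + 30 days result stands apart from the other group's Day 30 result. Laboratory results are also by group and sampling time (Protocol Section 11.8).
- **Day 0 already comes first.** Pooling is the second step, is not compared with control, and all analyses are descriptive.
- **Amendment 2 describes the test as keeping infected children from entering the study.** That is an entry purpose. Section 1.3.2 nevertheless speaks of clearing infection before vaccination, and the rationale concerns ChAd3-EBO-Z, which this group does not receive until Month 6.
- **Day 0 is not perfectly clear of malaria either.** The test may be 30 days old, and no repeat test is required after treatment.
- **The table shells may show a split.** The SAP derives dose at onset for solicited AEs as vaccine by occasion (Section 15.2.1). The SAP text promises no table that uses it in this way.

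The first two points narrow the concern to the AE tables. They also strengthen the fix, because the comparator exists and is left out of those tables.

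**Conclusion.** The point holds in a limited form. Malaria is tested and treated at Screening only, half of the pooled ChAd3-EBO-Z recipients are dosed 5 to 8 months later, and SAP v2.0 gives no separate view of solicited and unsolicited AEs after either Month 6 vaccine. This falls short of primary endpoints defined after each vaccination in both groups. It rests on the planned group sizes and on the SAP text, since the shells are not among the documents.

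Two stronger readings should be resisted. A reader might infer that the pooled result is biased by a definite amount, or that season is confounded with occasion. The documents give no prevalence, no effect of infection and no vaccination dates, so neither size nor direction follows. A reader might also infer that the main safety comparison or the secondary endpoint is compromised. The Day 0 comparison is randomised between groups screened alike, and the Month 6 + 30 days anti-GP result is already shown separately.

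**What to change.** In SAP v2.0 Sections 6.3.1, 15.1.2 and 15.2.2, present solicited and unsolicited AE incidence with exact 95% CIs in four columns: ChAd3-EBO-Z Day 0, ChAd3-EBO-Z Month 6, Nimenrix Day 0 and Nimenrix Month 6. Place these beside the pooled column, by age stratum and overall. Solicited AEs can use the dose-at-onset variable in Section 15.2.1, and unsolicited AEs the most-recent-vaccination variable in Section 15.1.1.

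Use the Month 6 Nimenrix column as the concurrent comparator for background events. Note that the study may be single-blind by then (Protocol Section 5.3). State that Month 6 doses were given without a malaria test, so the pooled result is supportive.

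The sponsor should reconcile Protocol Sections 1.2.2.1 and 1.3.2 with Table 5 and Section 6.6 on malaria status at the Month 6 dose, or explain why the stated concern does not apply there. No clinical rule is proposed. A further test at Month 6 would be a new procedure, and the documents do not settle how a positive result would be handled.

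The cost is SAP wording and extra table columns, with no new data, visits or subjects. The downside is that the 600-subject result is no longer read on its own.
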